### Primary End Point Assessment

Incidence of periprocedural embolic events –TIA/CVA/other systemic embolic events immediately after the left ventricular arrhythmia ablation up to 30 days post left ventricular arrhythmia ablation.

The incidence of new asymptomatic cerebrovascular events as documented by MRI at 24-48 hours post procedure and at 30 days after the left ventricular arrhythmia ablation.

### Secondary End Point Assessments

- A. Major bleeding events as defined above using TIMI criteria
- B. Minor Bleeding events as defined by the TIMI criteria

- C. Cardiovascular mortality
- D. All-Cause mortality
- E. Any other adverse events occurring during the study period

## **ADVERSE EVENTS**

An Adverse Event [AE] is defined as any new untoward medical occurrence or worsening of a pre-existing medical condition in a patient or clinical investigation subject administered an investigational (medicinal) product and that does not necessarily have a causal relationship with this treatment. An AE can therefore be any unfavorable and unintended sign (including an abnormal laboratory finding, for example), symptom, or disease temporally associated with the use of investigational product, whether or not considered related to the investigational product.

The causal relationship to study drug is determined by a physician and should be used to assess all adverse events (AEs). The causal relationship can be one of the following:

- Related: There is a reasonable causal relationship between study drug administration and the AE.
- Not Related: There is not a reasonable causal relationship between study drug administration and the AE.

The term “reasonable causal relationship” means there is evidence to suggest a causal relationship.

Adverse events can be spontaneously reported or elicited during open-ended questioning, examination, or evaluation of a subject. (In order to prevent reporting bias, subjects should not be questioned regarding the specific occurrence of one or more adverse events).

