#### **STUDY END POINTS:**

##### **Primary Objectives**

Primary end point: To estimate the new symptomatic (Stroke and TIA) and asymptomatic CVEs (brain MRI lesions) and systemic thromboembolism in patients undergoing left ventricular arrhythmia ablation with a novel oral anticoagulant ( DOAC) when compared to aspirin only.

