### **Neurology Evaluations**

Patients will undergo a NIHSS and EQ5D prior to procedure (within 24 hours) and post (12-48 hours). If changes in the NIHSS score of greater than 3 a neurologist will be consulted, and the patient will be evaluated and treated based on their recommendation. Asymptomatic Cerebrovascular emboli are defined as cerebral infarct present on MRI or CT scan for which no corresponding symptoms were documented [2]. Symptomatic Cerebrovascular emboli were defined as an episode of neurological dysfunction associated with a focal cerebral infarction in the region correlating with the dysfunction. .

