## STUDY ASSESSMENTS AND PROCEDURES

### Study Schematic

#### Time and Events Schedule

Procedure	Baseline (Within 30 days of the procedure)	Randomization (Within 48 prior to procedure)	Prior to Procedure (Within 24 hours of procedure)	Day of Procedure	24-48 hours Post- Procedure	Discharge	Day 30 (+/- 7 days) Follow- Up
Eligibility Assessments							
Informed Consent	X						
Medical History	X						
Inclusion/Exclusion Criteria	X						
Study Assessments:							
Physical Examination	X			X	X	X	X
Vital Signs	X		X	X	X	X	X
Adverse Events Assessment	X	X	X	X	X	X	X
Evaluation of Bleeding Events	X		X	X	X	X	X
Laboratory Tests	X						
Pregnancy Test	X						
Ablation Procedure				X			
Device Interrogation			X		X	X	X
Cerebral MRI					X		X
Neurology Evaluation NIHSS			X		X		X
EQ5D Survey			X		X		X
Randomization		X					
Dispense Study Drug				X (3 hours post hemostasis)			
Drug Compliance			X	X	X	X	X

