### Day of Procedure

- Physical Exam
- Vital Signs
- Adverse Event Assessment
- Dispense Study Drug
- Evaluation of Bleeding events – including TIMI evaluation
- Ablation Procedure

Post Procedure (within 24-48 hours)

- Physical Exam
- Vital Signs
- Adverse Event Assessment
- Evaluation of Bleeding events – including TIMI evaluation
- Device Interrogation
- Cerebral MRI
- Neurology Evaluation – NIHSS
- EQ5D Survey

Discharge

- Physical Exam
- Vital Signs
- Adverse Event Assessment
- Evaluation of Bleeding events – including TIMI evaluation Device Interrogation

Day 30 Follow up (+/- 7 days)

- Physical Exam
- Vital Signs
- Adverse Event Assessment
- Evaluation of Bleeding events – including TIMI evaluation
- Device Interrogation
- Cerebral MRI
- Neurology Evaluation – NIHSS
- EQ5D Survey

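### Resolved TIA and non-cerebral embolism count toward the primary endpoint but are captured only through non-directed adverse event reporting

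*Combined protocol and SAP*

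**What the plan says.** Under Primary Objectives the aim is "To estimate the new symptomatic (Stroke and TIA) and asymptomatic CVEs (brain MRI lesions) and systemic thromboembolism", DOAC against aspirin. Primary End Point Assessment splits this into a clinical part, "TIA/CVA/other systemic embolic events immediately after the left ventricular arrhythmia ablation up to 30 days post left ventricular arrhythmia ablation", and an imaging part, new asymptomatic lesions "documented by MRI at 24-48 hours post procedure and at 30 days after the left ventricular arrhythmia ablation".

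For the clinical part, the Time and Events Schedule marks "Neurology Evaluation NIHSS" before the procedure, at 24-48 hours and at day 30. Neurology Evaluations adds: "If changes in the NIHSS score of greater than 3 a neurologist will be consulted". That section describes a symptomatic event as neurological dysfunction with a focal infarct in the matching region. TIA and systemic embolism are not defined anywhere.

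Bleeding has its own line, "Evaluation of Bleeding events – including TIMI evaluation", at every visit except randomization, and Safety Assessments gives graded TIMI definitions. Embolic symptoms have no such line.

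Adverse event assessment is marked in all seven schedule columns. The Adverse Events section accepts spontaneous reports, open-ended questions, examination and evaluation. It then says that "subjects should not be questioned regarding the specific occurrence of one or more adverse events", giving prevention of reporting bias as the reason. It does not exempt endpoint events.

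**The concern.** A patient who has a short episode of speech loss on day 12 and has recovered by day 30 has had a primary event. At day 30 the NIHSS shows no change. No visit form asks about such an episode, and read literally the protocol discourages the coordinator from asking. The event enters the data only if the patient mentions it in answer to an open question. Even then, without a matching infarct it does not fit the description of a symptomatic event in Neurology Evaluations. An embolus to a limb or an abdominal organ is likewise outside what NIHSS and brain MRI assess.

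No placebo is described, and only the radiologist reading the MRI is described as blinded (Cerebral MRI). What patients mention, and what staff follow up, may therefore depend on knowing the arm. The clinical part of the primary endpoint could be under-counted, and unequally so. The Statistical analysis paragraph makes a larger study depend on a positive signal from this one.

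**Working it through.** **Which scheduled item can find which event**

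| Scheduled item | When | Resolved TIA | Non-cerebral embolism |
|---|---|---|---|
| NIHSS | before procedure, 24-48 h, day 30 | no, scores the deficit present | no |
| Brain MRI | 24-48 h, day 30 | only if it left a lesion | no |
| Bleeding evaluation | every visit except randomization | no | no |
| Physical examination | baseline, procedure day, 24-48 h, discharge, day 30 | no, if signs have gone | if signs persist |
| Adverse event assessment | all seven columns | if volunteered or raised by an open question | same |

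The Adverse Events section counts examination among the ways an adverse event is found, so the last two rows are one route, and it is not directed at embolic symptoms. A TIA that leaves a lesion would still enter the primary endpoint through MRI, though possibly labelled asymptomatic. The events at risk are TIAs without a lesion and emboli outside the brain.

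**Definition**

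Primary Objectives and Primary End Point Assessment both count TIA. Neurology Evaluations requires a focal infarction. A TIA without infarction counts under the first two and fails the third.

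**Expected number**

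The plan gives no expected number of clinical events, so there is no figure to reproduce. Inputs:
- 50 patients analysed, 25 per arm (Sample Size Justification);
- 2.3% symptomatic cerebrovascular events after AF ablation, 41% of them TIA (Overall Risk/Benefit Assessment). Applying these to left ventricular ablation is an assumption.

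Results:
- Symptomatic events: 50 × 0.023 = 1.15.
- TIA rate: 0.023 × 0.41 = 0.00943; expected TIAs: 50 × 0.00943 = 0.47.
- Chance of at least one TIA: 1 − (1 − 0.00943)^50 = 0.38.
- One event in one arm: 1/25 = 4 percentage points.

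The documents give no rate for non-cerebral embolism and no share of TIAs that would be missed. The 0.47 is thus the most that could be lost among TIAs at this rate.

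**Effect on power**

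The plan states no alpha, power or control rate. As an illustration, take 40% against 10%, two-sided alpha 0.05 and n = 25 per arm, with

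power = Φ{ [ |p1 − p2|√n − 1.96 √(2 p̄(1 − p̄)) ] / √[p1(1 − p1) + p2(1 − p2)] }.

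- All events found: (1.500 − 1.200)/0.574 = 0.522, power 69.9%.
- Every TIA missed, with the loss proportional in the two arms: p1 = 0.40 − 0.00943 = 0.3906 and p2 = 0.10 − 0.25 × 0.00943 = 0.0976. Then (1.465 − 1.191)/0.571 = 0.480, power 68.4%.

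The loss is 1.5 percentage points.

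**The case against.** The strongest reply is that the plan does have a route to these events. Adverse event assessment takes place at every visit, open-ended questioning is itself active elicitation, physical examinations are repeated, and all SAEs are collected to 30 days after dosing. This stands. A reader might infer that nothing in the plan can detect a resolved event, or that NIHSS is the only tool; the schedule does not support either. It is also too strong to say that direct questions are forbidden: the text says they should not be asked, in a paragraph on eliciting adverse events, and bleeding is evaluated specifically under the same rule. What is left is that embolic symptoms have neither a schedule row nor an exemption.

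Other tempting readings also fail:
- **The NIHSS trigger limits the endpoint.** It governs referral to a neurologist. Smaller changes are still recorded at the scheduled NIHSS.
- **Day 30 is the only contact after discharge.** Secondary Objectives mentions a 1-week minor bleeding assessment that the schedule omits. That is a conflict to reconcile, not proof of no contact.
- **Up to 1.5 TIAs are expected.** This needs 50 × 7.5% × 41%. But the 2.7% and 7.5% are stroke rates after ventricular ablation, in a range that starts at 0; the 41% is a share of symptomatic events after AF ablation. The denominators differ.
- **Bleeding is measured better overall.** Embolism has two MRIs with a blinded reader, while laboratory tests are scheduled only at baseline although TIMI grading rests largely on haemoglobin falls. The contrast holds for symptom review only.

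It is also fair that MRI lesions will probably dominate the endpoint. On the AF-ablation figures, 50 × 14% = 7 asymptomatic events stand against 1.15 symptomatic ones, and this is a pilot. Finally, direct questions in a trial without blinded clinical assessment can themselves draw arm-dependent answers. Identical wording in both arms limits that risk but does not remove it.

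**Conclusion.** The point holds as a weakness in ascertainment. Two components of the primary endpoint, resolved TIA and embolism outside the brain, depend on non-directed reporting. The adverse event rule discourages specific questions without exempting endpoint events, and the description of a symptomatic event leaves out a TIA without a lesion.

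The numerical effect is small: about 0.5 expected TIA in 50 patients, and roughly 1.5 points of power in the illustration even if all were missed. The count rests on carrying the AF-ablation figures over; the power figure also rests on the assumed 40% against 10%. The issue is validity: with 25 per arm, one event noticed in one arm and not in the other shifts the comparison by 4 points. The documents do not show that reporting will differ by arm; they leave it possible. Severity: should-fix.

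**What to change.** 1. In Adverse Events, state that the rule against specific questions does not apply to primary-endpoint events.
2. In the Time and Events Schedule and the visit lists, add at 24-48 hours, discharge and day 30 one fixed, identically worded set of questions on symptoms of TIA, stroke and systemic embolism since last contact, asked in both arms.
3. Reconcile Neurology Evaluations with Primary Objectives and Primary End Point Assessment so that a TIA without infarction counts. Classify any new focal deficit as a candidate event whatever the NIHSS change. The referral trigger to the neurologist stays as it is.

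The NIHSS timing should be aligned in the same edit: Neurology Evaluations gives a 12-48 hour post-procedure window and no day 30 test, while the schedule gives 24-48 hours and day 30.

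The cost is a few questions at visits that already take place, one CRF page and a wording change. The downsides are more non-specific symptoms to classify, and prompted answers that knowledge of the arm can still influence.

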### **Serious Adverse Events**

**Serious Adverse Event (SAE)** is any untoward medical occurrence at any dose that:

- results in death

- is life-threatening (defined as an event in which the subject was at risk of death at the time of the event; it does not refer to an event which hypothetically might have caused death if it were more severe)
- requires inpatient hospitalization or causes prolongation of existing hospitalization (see **NOTE\***: below for exceptions)
- results in persistent or significant disability/incapacity
- is a congenital anomaly/birth defect
- is an important medical event, defined as a medical event that may not be immediately life-threatening or result in death or hospitalization but, based on appropriate medical and scientific judgment, may jeopardize the subject or may require intervention (e.g., medical, surgical) to prevent one of the other serious outcomes listed above. Examples of such events include but are not limited to intensive treatment in an emergency department or at home for allergic bronchospasm; blood dyscrasias or convulsions that do not result in hospitalization.
- Potential drug-induced liver injury (DILI) is also considered an important medical event-- see the DILI section below for a definition of a potential DILI event.
- Suspected transmission of an infectious agent (eg, pathogenic or non-pathogenic) via the study drug is an SAE.
- Although pregnancy, overdose, and cancer are not always serious by regulatory definition, these events must be handled as SAEs.

**\*NOTE:** *The following hospitalizations are not considered SAEs:*

- A visit to the emergency room or other hospital department lasting less than 24 hours that does not result in admission (unless considered an “important medical event” or a life-threatening event)
- Elective surgery planned before signing consent
- Admissions as per protocol for a planned medical/surgical procedure
- Routine health assessment requiring admission for baseline/trending of health status (eg, routine colonoscopy)
- Medical/surgical admission other than remedying ill health state that was planned before study entry. Appropriate documentation is required in these cases
- Admission encountered for another life circumstance that carries no bearing on health status and requires no medical/surgical intervention (eg, lack of housing, economic inadequacy, caregiver respite, family circumstances, administrative reason)
- In this study, the following adverse events are to be reported to BMS, regardless of whether these reports are classified as serious or unexpected:

Potential or suspected cases of liver injury including but not limited to liver test abnormalities, jaundice, hepatitis or cholestasis.

### ***Serious Adverse Event Collecting and Reporting***

Following the subject's written consent to participate in the study, all SAEs, whether related or not related to study drug, must be collected, including those thought to be associated with protocol-specified procedures. All SAEs must be collected that occur during the screening period and within 30 days of discontinuing dosing. If applicable, SAEs must be collected that relate to any later protocol-specific procedure (such as follow-up skin biopsy).

The investigator should report any SAE occurring after these time periods that is believed to be related to study drug or protocol-specified procedure.

An SAE report should be completed for any event where doubt exists regarding its status of seriousness.

If the investigator believes that an SAE is not related to study drug, but is potentially related to the conditions of the study (such as withdrawal of previous therapy, or a complication of a study procedure), the relationship should be specified in the narrative section of the SAE Report Form.

SAEs, whether related or unrelated to the study drug, and pregnancies must be reported to BMS within 24 hours. SAEs must be recorded on the SAE Report Form; Pregnancies on a Pregnancy Surveillance Form.

**SAE Email Address:** [contact]

**SAE [contact]

If only limited information is initially available, follow-up reports are required. (Note: Follow-up SAE reports should include the same investigator term(s) initially reported.)

All SAEs should be followed to resolution or stabilization.

### ***SAE Reconciliation***

The investigator will reconcile the clinical database SAE cases transmitted to the study team. The DSMB and study steering committee will adjudicate the adverse events in the event of disagreement.

## **Non-Serious Events**

A non-serious adverse event is an AE not classified as serious.

### ***Non-Serious Adverse Events (NSAEs) Collecting and Reporting***

The collection of non-serious adverse event (NSAE) information should begin at initiation of study drug. Non-serious adverse event information should also be collected from the start of a placebo lead-in period or other observational period intended to establish a baseline status for the subjects.

Non-serious AEs should be followed to resolution or stabilization, or reported as SAEs if they become serious. Follow-up is also required for non-serious AEs that cause interruption or discontinuation of study drug, or those that are present at the end of study treatment as appropriate.

### **Laboratory Test Abnormalities**

The following laboratory abnormalities should be captured and reported as appropriate:

- Any laboratory test result that is clinically significant or meets the definition of an SAE
- Any laboratory test result abnormality that required the subject to have study drug discontinued or interrupted
- Any laboratory test result abnormality that required the subject to receive specific corrective therapy.

It is expected that wherever possible, the clinical rather than the laboratory term will be used by the reporting investigator (eg, use the term anemia rather than low hemoglobin value).

Laboratory test abnormalities are provided to BMS via annual safety reports (if applicable), and interim or final study reports.

## **Pregnancy**

If, following initiation of the investigational product, it is subsequently discovered that a study subject is pregnant or may have been pregnant at the time of investigational product exposure, including during at least 5 half-lives after product administration, the investigational product will

be permanently discontinued in an appropriate manner (eg, dose tapering if necessary for subject safety).

The investigator must immediately notify [contact] of this event via the Pregnancy Surveillance Form within 24 hours and in accordance with SAE reporting procedures.

Follow-up information regarding the course of the pregnancy, including perinatal and neonatal outcome and, where applicable, offspring information must be reported on a Pregnancy Surveillance Form.

Any pregnancy that occurs in a female partner of a male study participant should be reported to BMS. Information on this pregnancy may also be collected on the Pregnancy Surveillance Form.

Protocol-required procedures for study discontinuation and follow-up must be performed on the subject unless contraindicated by pregnancy (eg, x-ray studies). Other appropriate pregnancy follow-up procedures should be considered if indicated.

### **Overdose**

An overdose is defined as the accidental or intentional administration of any dose of a product that is considered both excessive and medically important. All occurrences of overdose must be reported as SAEs.

### **Potential Drug-Induced Liver Injury (DILI)**

Wherever possible, timely confirmation of initial liver-related laboratory abnormalities should occur prior to the reporting of a potential DILI event. All occurrences of potential DILIs, meeting the defined criteria, must be reported as SAEs.

Potential drug induced liver injury is defined as

1. AT (ALT or AST) elevation  $> 3$  times upper limit of normal (ULN)

AND

2. Total bilirubin  $> 2$  times ULN, without initial findings of cholestasis (elevated serum alkaline phosphatase),

AND

3. No other immediately apparent possible causes of AT elevation and hyperbilirubinemia, including, but not limited to, viral hepatitis, pre-existing chronic or acute liver disease, or the administration of other drug(s) known to be hepatotoxic.

### **Other Safety Considerations**

Any significant worsening noted during interim or final physical examinations, electrocardiograms, x-rays, and any other potential safety assessments, whether or not these procedures are required by the protocol, should also be recorded as a non-serious or serious adverse event, as appropriate, and reported accordingly.

### **DATA MONITORING COMMITTEE**

To meet the study's ethical responsibility to its subjects, an independent data safety monitoring Board (DSMB) will monitor results during the study. The board consists of 2 physicians and 1 statistician who have no formal involvement or conflict of interest with the subjects or the investigators. Records will be reviewed after the first 50 patients and then at the completion of the study.

If the major bleeding events in the DOAC group occur at >15% but <30% (absolute event rate) of those in the ASA group during any of the assessments, a recommendation will be made to consider modifying the study by the members of the DSMB. First consideration to modify is to decrease the dose of the drug to 2.5mg PO twice daily. If the major bleeding events in the DOAC group occur at >30% (absolute event rate) of those in the ASA group during any of the assessments, a recommendation will be made to stop the study by the members of the DSMB.

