## **INVESTIGATIONAL PLAN**

### **Study Design and Duration**

This is a multicenter, randomized, prospective study to determine, if DOAC can be used periprocedural in patients undergoing a scar left ventricular arrhythmia ablation. Patients will be screened from both the clinic setting and upcoming EP lab schedule. The patient's chart will be reviewed and those that meet inclusion/exclusion will be approached for the study. For this study, we intend to enroll 52 consecutive subjects who are undergoing a scar left ventricular arrhythmia ablation at participating institutions if they meet all other inclusion criteria and do not have any exclusion criteria. Patients will be randomized in a 1:1 fashion.

Figure 1 shows the use of ASA or DOAC for left ventricular arrhythmia ablation.

[figure not shown]
Patients undergoing left ventricular arrhythmia ablation will be consented and randomized to either ASA 81 mg or 100 mg daily or DOAC twice daily. Patients randomized to ASA will continue or start ASA 81 mg or 100 mg by mouth daily, and continue up to 30 days after the procedure. Patients randomized to DOAC group will stop the ASA if they are currently taking it; DOAC 5 twice daily will be started 3 hours after hemostasis and continue for 30 days post procedure.

The drugs to which they are assigned to will be continued at least for 30 days post left ventricular arrhythmia ablation. All subjects will be followed from baseline to 30 days post procedure. At this time they will have completed the study and can stop either DOAC and/or Aspirin at the physician's discretion.

*Final revised protocol*

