### **STATISTICAL CONSIDERATIONS**

#### ***Study Management and Sample Size Justification***

This is a pilot study and 52 total patients will be enrolled in the study. We expect to analyze a total of 50 patients and each arm will consist of 25 patients. The additional 2 allows for attrition. Since this is a pilot study, the number needed to treat to achieve a pre-specified statistical significance cannot be calculated accurately. Exact sample size could not be given due to lack of pre-existing data on this subject. We hypothesize a 30% difference in outcomes can be seen with a total sample size of 50 patients.

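### The only interim DSMB review comes after 50 of 52 patients, too late for its dose-cut and stopping rules to reach most of the trial

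*Combined protocol and SAP*

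**What the plan says.** The Data Monitoring Committee section sets up an independent board of two physicians and a statistician to monitor results while the study runs, and grounds this in the ethical duty to subjects. It then gives the timetable: "Records will be reviewed after the first 50 patients and then at the completion of the study".

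Two rules on major bleeding in the DOAC arm follow. If events "occur at >15% but <30% (absolute event rate) of those in the ASA group during any of the assessments", then "a recommendation will be made to consider modifying the study by the members of the DSMB". The section adds: "First consideration to modify is to decrease the dose of the drug to 2.5mg PO twice daily". If events "occur at >30% (absolute event rate) of those in the ASA group during any of the assessments", the board is to recommend stopping. Both rules apply at the scheduled assessments.

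On size, Study Management and Sample Size Justification says: "This is a pilot study and 52 total patients will be enrolled in the study". It continues: "We expect to analyze a total of 50 patients and each arm will consist of 25 patients". The other two patients cover attrition. Allocation is 1:1.

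On exposure, Study Design and Duration says: "The drugs to which they are assigned to will be continued at least for 30 days post left ventricular arrhythmia ablation".

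**The concern.** A rule that lowers the dose or stops the trial protects only patients who have yet to start drug or are still taking it. With 52 patients planned and the first look after 50, nearly all DOAC patients will have started at the full dose, and many will have finished, before the board sees bleeding by arm. The second review is at completion, when nobody is left to protect.

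Major bleeding is the foreseeable harm here. The protocol says that oral anticoagulation after this ablation is not standard of care. DOAC starts 3 hours after hemostasis, following heparin during the procedure, and epicardial access is allowed. The Statistical analysis paragraph describes the pilot as a study of feasibility and safety. An independent comparison of bleeding by arm is the board's main contribution, and the timetable leaves it little room to act.

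**Working it through.** **Inputs from the protocol.** Enrolment 52; analysis set 50 (25 per arm); attrition allowance 2; allocation 1:1; interim review after 50; drug course 30 days; triggers at 15% and 30%.

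**Inputs the protocol does not give.** Accrual rate and major bleeding rates. Both are assumed below and shown over a range.

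**1. The plan's own figure.** 2 × 25 + 2 = 52. It reproduces.

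**2. Position of the interim look.** 50/52 = 96.2% enrolled. Not yet enrolled: 52 − 50 = 2 (3.8%), about 1 on DOAC.

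**3. Patients still on drug at the look.** With even accrual over M months and a course of about one month, the number on drug is about 52/M, half of them on DOAC.

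- M = 6: 8.7 (about 4 on DOAC)
- M = 12: 4.3 (about 2 on DOAC)
- M = 24: 2.2 (about 1 on DOAC)

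Adding the 2 unenrolled gives about 11 of 52 (21%) within reach at 6 months of accrual and about 4 of 52 (8%) at 24 months. This assumes a prompt review at the 50th enrolment. If the 50 must first finish 30 days, at most the remaining 2 are within reach.

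**4. Other routes to the board.** Dose Modifications and Discontinuation of Subjects from Treatment let investigators act patient by patient. Bleeding is assessed at most visits. SAEs go to the drug company within 24 hours, with no stated route to the board. Under SAE Reconciliation the board adjudicates adverse events only when there is disagreement. None of these is an earlier review by arm, and no unscheduled-review trigger is given.

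**5. A look at 26 instead.** Not yet enrolled: 52 − 26 = 26 (50%), about 13 on DOAC; fewer if recruitment continues while data are gathered.

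**6. What the earlier look costs in precision.** The trigger is taken as an observed DOAC-minus-ASA difference above 15 points. Its probability is the sum of Bin(x; n₁, p₁) × Bin(y; n₀, p₀) over all x, y with x/n₁ − y/n₀ > 0.15. This assumes complete 30-day data.

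| DOAC/ASA patients | 5% vs 2% | 10% vs 2% | 20% vs 2% |
|---|---|---|---|
| 13/13 | 0.109 | 0.319 | 0.698 |
| 12/14 | 0.094 | 0.282 | 0.648 |
| 11/15 | 0.079 | 0.244 | 0.593 |
| 15/11 | 0.030 | 0.158 | 0.548 |
| 14/12 | 0.024 | 0.133 | 0.494 |
| 25/25 | 0.023 | 0.176 | 0.672 |

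Only the last column has a true difference (18 points) above the line. In the first two columns, firing is over-triggering.

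False signals at equal true rates of 2%, 5% and 10% have probability 0.021, 0.079 and 0.154 at 13/13, against 0.001, 0.012 and 0.048 at 25/25. A stop signal (above 30 points) at 20% vs 2% has probability 0.215 at 13/13, against 0.082 at 25/25.

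**7. Trigger wording.** The phrase can mean the DOAC-arm rate or the DOAC-minus-ASA difference. With 4 DOAC and 1 ASA major bleeds at 25 per arm, the arm rate is 4/25 = 16% (consider modifying) and the difference is 16% − 4% = 12 points (no action). With ASA at 2% and DOAC at 10%, 20% and 30%, the two readings lead to different actions with probability 0.06, 0.12 and 0.11 at 25 per arm, almost always by one step.

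**The case against.** Three arguments on the other side carry weight.

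First, the timing biases no estimate or test, and the exposure is small: about 26 patients for 30 days. Patients with active bleeding, bleeding disorders, contraindications to anticoagulation or creatinine clearance of 40 or below are excluded, and reduced-dose criteria exist. No blinding of treatment is described, so site staff can link a bleed to an arm as it happens and act on it. This stands. It lowers the severity but does not supply an independent comparison.

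Second, a reader might infer that the board could protect almost no one. The documents do not support that, because accrual is not stated. Under fast accrual and a prompt look, about 9 patients could still be on drug in addition to the 2 unenrolled.

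Third, a reader might infer that waiting until 50 adds almost no information, since 13/13 gives 0.698 against 0.672 at 25/25. That rests on the most favourable split: 2/13 = 15.4% only just clears the line. The other splits checked give 0.49 to 0.65. Exact balance at 26 is not assured, because randomization is stratified by site and no block scheme is stated. Incomplete follow-up at the look would lower detection somewhat further. The 20% rate also has no anchor in the documents. At 5% vs 2% the earlier look mostly adds unwarranted signals (0.109 at 13/13 against 0.023). The move to 26 is therefore a trade-off, and 26 is a choice.

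On the trigger, the wording might be read as a ratio to ASA events, so that 4 against 1 (400%) would mean stop. The words "absolute event rate" in the rule speak against that.

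**Conclusion.** The concern holds as a matter of timing. The one interim DSMB review comes at 96% of enrolment, and the dose-cut and stopping rules are tied to it. They can reach at most 2 unenrolled patients (about 1 on DOAC) plus about 2 to 9 still on drug, on the assumption of even accrual over 24 to 6 months and a review at the 50th enrolment. The limit of 2 unenrolled needs no assumption about accrual or bleeding rates.

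This should be fixed because the remedy is cheap and restores the purpose the protocol gives the board. It does not invalidate the trial: investigator-level safeguards remain and no analysis is affected. The trigger wording is a minor clarification, since its two plausible readings seldom lead to different actions.

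**What to change.** In the Data Monitoring Committee section, replace the review after 50 patients with one DSMB review of bleeding by arm when about 26 patients have been treated, using data to date. Keep the review at completion.

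As a minor clarification, state the trigger as the DOAC-minus-ASA difference in observed TIMI major bleeding proportions on the actual arm sizes: above 15 and up to 30 points, consider modifying; above 30 points, recommend stopping.

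The cost is protocol wording. The board still meets twice, and a safety-only look needs no efficacy alpha adjustment. The price is a noisier look. At 20% vs 2%, the probability that the trigger fires is 0.49 to 0.70 depending on the split (0.67 at 25 per arm), somewhat less with incomplete follow-up. At 13 per arm and equal rates of 2% to 10%, false signals rise to 0.02–0.15 (from 0.001–0.05). This is acceptable because the board only recommends and can weigh small counts.
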